### 6.5.2.1 30-day Follow-Up

The 30-day follow-up visit will occur 30 days (+21 days) post-index procedure, and will include the following assessments:

1. Physical exam (weight, heart rate, blood pressure)
2. Modified Rankin Scale (mRS)
3. NIH Stroke Scale (NIHSS)
4. Barthel Index
5. Echocardiography
6. 12 lead ECG (for subjects receiving a new permanent pacemaker, ECG should be completed showing the underlying rhythm as well as the current pacing programming)
7. Lab Measurements (including CBC and Platelet count, BUN and creatinine, BNP or ProBNP, INR if subject is on coumadin, warfarin or other anticoagulants/vitamin K antagonists in lieu of warfarin, Troponin or CK/CK-MB and Albumin)
8. NYHA Functional Classification
9. Frailty Index Assessment (Katz Index of Activities of Daily Living, Grip Strength, 5 meter walk test)
10. Quality of Life Assessment (SF-36)
11. MMSE-2:SV
12. Six Minute Walk Test (6MWT)
13. Cardiovascular medications documentation
14. Adverse events assessment

### 6.5.2.2 12-Month Follow-Up

The 12-month follow-up visit will take place at 12 months (365 days -30 /+45 days) post-index procedure, and will include the following assessments:

1. Physical exam (weight, heart rate, blood pressure)
2. Modified Rankin Scale (mRS)
3. NIH Stroke Scale (NIHSS)
4. Barthel Index
5. Echocardiography
6. 12 lead ECG (for subjects receiving a new permanent pacemaker, ECG should be completed showing the underlying rhythm as well as the current pacing programming)
7. Lab measurements (including CBC and Platelet count, BUN and creatinine, BNP or ProBNP, INR if subject is on coumadin, warfarin or other anticoagulants/vitamin K antagonists in lieu of warfarin, Troponin or CK/CK-MB and Albumin)

## Clinical Investigation Plan

8. NYHA Functional Classification
9. Frailty Index Assessment (Katz Index of Activities of Daily Living, Grip Strength, 5 meter walk test)
10. Quality of Life Assessment (SF-36)
11. MMSE-2:SV
12. Six Minute Walk Test (6MWT)
13. Cardiovascular medications documentation
14. Adverse events assessment

### 6.5.2.3 Annual Follow-up

The following data should be collected at years 2, 3, 4 and 5 years ( $\pm$  60 days) post index procedure (note: remote follow-up either in-home or by phone may be conducted):

1. Physical exam (if an in-person office visit is conducted)
2. NYHA Functional Classification (if an in-person office visit is conducted)
3. Cardiovascular medications
4. Adverse event assessment
5. Modified Rankin Stroke Scale (if an in-person office visit is conducted)
6. Echocardiography (required at 2-year, 4-year, and 5-year follow-up visits)

**Note:** if the 12-month or annual follow-up visits are conducted prior to the nominal due date (e.g., before day 365 for the 12-month visit), it may be requested to conduct a vitality status check to document the subject's status prior to the next follow-up visit.

### 6.5.3 Unscheduled Follow-up

#### 6.5.3.1 Unscheduled Follow-Up Visits for Evaluation of Suspected Neurological Event

If the subject experiences a neurological event (e.g., trans-ischemic attack (TIA), stroke, or encephalopathy) within 2 years post implantation, the event should be documented on an adverse event form and further evaluation should be performed at an unscheduled visit 90 days ( $\pm$ 14 days) from the date of the neurological event. The unscheduled visit will include the following assessments:

- Neurological Assessment conducted by a neurologist or a neurology fellow
- Modified Rankin Score (mRS)
- NIH Stroke Scale

Refer to Appendix X for a copy of the Modified Rankin Score and APPENDIX XI for a copy of the NIH Stroke Scale.

#### 6.5.3.2 Unscheduled Follow-Up Visits Including an Echocardiographic Assessment

All echocardiograms performed as part of an unscheduled visit will be analyzed by the echocardiographic core laboratory. See Section 3.2.5 for detailed information on site responsibility.

## Clinical Investigation Plan

### 6.5.4 Patient Reported Outcome (PRO) Measures

The following PRO measures will be collected according to the CIP requirements to assess whether the health of subjects has improved since enrollment in the clinical study:

- SF-36
- Mini-Mental State Examination (MMSE-2)
- New York Heart Association Functional Classification
- Barthel Index

The Principal Investigator, research coordinator or study designee will administer the patient-reported outcome (PRO) measures. It is important the subject understands the meaning of all words and instructions in the measures. The subject should be instructed to ask any questions about the measures if further explanation is needed. Once the PRO measures are completed, the research coordinator or study designee will review for completeness to verify that all questions have been answered according to the directions provided.

#### 6.5.4.1 SF-36

The Medical Outcomes Study Questionnaire Short Form 36 Health Survey version 2 (SF-36 v2) is a widely used, validated questionnaire that provides an indicator of overall health status. The self-administered questionnaire consists of 10 items across eight separate domains (Vitality, Physical functioning, Bodily pain, General health perceptions, Physical role functioning, Emotional role functioning, Social role functioning, Mental health). The questionnaire takes approximately five to 10 minutes to complete; elderly subjects may require 15 minutes.

Two sets of scores are derived from the SF-36; eight individual domain scores, and two summary scores, one for the physical component (PCS) and one for the mental component (MCS) summary scores. For each set of scores, two alternative approaches may be used in calculating scores: a normal, additive approach that produces 0-to-100 scores for the eight scales (with a lower score indicating more disability and higher scores less disability), and a norm-based approach that adjusts these raw scores to have a mean of 50 and a standard deviation of 10. Refer to Appendix VII for the sample questionnaire.

#### 6.5.4.2 Mini-Mental State Examination-2

The Mini Mental State Examination-2 (MMSE-2) is a validated, 11-question tool used to assess mental status. The MMSE-2 tests five areas of cognitive function: orientation, registration, attention and calculation, recall, and language. It takes 5-10 minutes to complete and must be administered using a script to the study subject.

The MMSE-2 begins with a graded assessment of orientation to place and time, followed by testing two aspects of memory (immediate recall for three objects presented orally, followed by a serial sevens task which is interposed to assess attention, concentration, calculation, and to prevent the individual from rehearsing the three objects previously learned). The third and final section surveys aphasia by testing functions of naming, repetition, understanding a three-stage command, reading, writing and copying a drawing. A maximum score of 30 is possible with a score of 23 or lower indicative of cognitive impairment. Refer to Appendix VIII for the sample questionnaire.

#### 6.5.4.3 New York Heart Association Functional Classification

The New York Heart Association (NYHA) Functional Classification is a validated tool used to classify the extent of heart failure in patients. It places patients in one of four categories based on how much they are limited during physical activity; the limitations/symptoms are in regard to normal breathing and varying

## Clinical Investigation Plan

degrees in shortness of breath and/or angina. The NYHA function classification remains the most important prognostic marker for heart failure in routine clinical use. The current version includes two sections: functional capacity NYHA Classification based on patient symptoms and an objective assessment based on physical exam and diagnostic tools. Refer to Appendix VI for the sample questionnaire.

### 6.5.4.4 Barthel Index

The Barthel Index for Activities of Daily Living (Barthel Index) is used to measure functional independence in activities of daily living (ADL). The validated tool takes approximately 5 minutes to complete and assesses 10 performance items describing ADL and mobility including: feeding, bathing, grooming, dressing, bowel control, bladder control, toilet use, transfers (bed to chair to back), mobility on level surfaces, stair use). Each performance item is rated on a scale with a given number of points assigned to each level or ranking with a higher number associated with a greater likelihood of being able to live at home with a degree of independence following discharge from the hospital. Total possible scores range from 0 – 100, with lower scores indicating increased disability. If used to measure improvement after treatment, changes of more than two points in the total score reflect a probable genuine change, and change on one item from fully dependent to independent is also likely to be reliable. Refer to Appendix IX for the sample questionnaire.

## Clinical Investigation Plan

### 6.5.5 Schedule of Events

Table 5 provides a tabulated schedule of the study-required activities and standard of care data collection in the clinical study.

Table 5: Table of Assessments

Study Activity	Screening	Baseline	Procedure	Discharge	30 days [+21 days]	12 months  [-30/+45 days]	Annual visits (2 through 5 years) [±60 days]
Subject Interview and Informed Consent	X						
Demographics	X						
Medical History	X						
Physical Exam	X			X	X	X	X 
NYHA Classification	X				X	X	X 
Cardiovascular Medications documentation		X		X	X	X	X
Coronary and Aortic Angiogram (with runoff if clinically indicated)	X (within 12 months prior to consent)						
National Institute of Health Stroke Scale (NIHSS)		X		X	X	X	
Modified Rankin Scale (mRS)		X		X	X	X	X 
Barthel Index		X		X	X	X	
MMSE-2:SV		X			X	X	
Neurological Assessment	A neurological assessment must be performed at 90 days (±14 days) from the date of a suspected neurological event within 2 years post implantation						
Surgical Risk Assessment (STS, EuroSCORE II)	X						
Six Minute Walk Test		X			X	X	
Frailty Index (Katz Index of ADLs, Grip strength, 5 m walk)	X				X	X	
FEV1	X (if clinically indicated)						
Non-Invasive Tests							
12 lead Electrocardiogram (ECG) 	X			X	X	X	
Cardiac rhythm monitoring			X				
Echocardiogram	X		X 	X 	X	X	X 
Angiogram			X				
3D Transesophageal Echocardiogram (TEE)	X  (if CT is contraindicated) TEE is also						

## Clinical Investigation Plan

Study Activity	Screening	Baseline	Procedure	Discharge	30 days [+21 days]	12 months  [-30/+45 days]	Annual visits (2 through 5 years) [±60 days]
	recommended after adverse events of ischemic stroke and myocardial infarction.						
CT Scan with Angiography for chest, abdomen and pelvis	X (within 12 months of consent)						
Chest X-Ray		X					
Quality of Life Measures							
SF-36		X			X	X	
Lab Measurements							
CBC and Platelet count	X			X	X	X	
BUN and Creatinine	X		X 	X	X	X	
BNP or ProBNP	X				X	X	
INR (if subject is on Coumadin or Warfarin  )		X			X	X	
Troponin or CK / CK-MB		X	X 	(X)	X	X	
Albumin (for Frailty Index)	X				X	X	
Other							
Adverse Event Assessment	X	X	X	X	X	X	X
Deviation	(X)	(X)	(X)	(X)	(X)	(X)	(X)
Device Deficiency			(X)	(X)	(X)	(X)	(X)
Withdrawal			(X)	(X)	(X)	(X)	(X)
Death	(X)	(X)	(X)	(X)	(X)	(X)	(X)

 In the event a 12 month visit per the requirements in the clinical investigational plan is not completed, the site may call the subject to document survival.

 For subjects receiving a new permanent pacemaker, ECG should be completed showing the underlying rhythm as well as the current pacing programming.

 Copy of echocardiographic exam to be stored at the site and available to the Sponsor upon request.

 To be done within 24-48 hours after procedure, or as close to discharge as possible (but no more than 7 days after procedure).

 If CT is contraindicated and/or not possible to be obtained for certain subjects, a 3D TEE and non-contrast CT of chest and abdomen/pelvis may be accepted if approved by the subject selection committee.

 To be collected within 72 hours **before** index procedure and within 72 hours **after** index procedure

 To be collected within 72 hours **before** index procedure and approximately 12-24 hours **after** the procedure, approximately 36-48 hours after the procedure, and at approximately 72 hours (or at discharge, if patient is discharged prior to 72 hours post procedure) to be consistent with VARC II guidelines.

 Subjects may take other anticoagulants/vitamin K antagonists in lieu of warfarin

 Only required if an in-person office visit is conducted

 Required at all annual follow-up visits except for the 3-year visit

(X) indicates if applicable

## Clinical Investigation Plan

### 6.6 Requirement for Core Laboratories

Independent core laboratories will be utilized for evaluating CT scans and echocardiograms collected in the clinical study. Each investigational site will submit CT scans and echocardiograms to the respective core laboratories for evaluation. The core laboratories will provide the study required interpretation and documentation of each data submission according to their Standard Operating Procedures and study specific charter.

Data obtained from the core laboratory readings will be used for study purposes only and not for clinical treatment of the subject. The Sponsor will use the data provided by the core laboratories in data analyses, where measurements were collected by the core laboratory. If the core laboratory determines that the imaging exam is unreadable, the site will be responsible for having the subject return for another assessment.

## 7 ADVERSE EVENTS

To comply with worldwide standards and guidelines on clinical study adverse event reporting, the Sponsor has adopted uniform and worldwide applicable standard definitions and reporting timelines to be used and adhered to by the investigators.

### 7.1 Definitions

#### 7.1.1 Adverse Event

An adverse event (AE) is any untoward medical occurrence, unintended disease or injury, or untoward clinical signs (including abnormal laboratory findings) in subjects, users or other persons, in the context of a clinical investigation, whether or not related to the investigational medical device.

As part of ISO14155 Section 3.2, the adverse event definition has the following notes:

Note 1: This definition includes events related to the investigational medical device or the comparator.

Note 2: This definition includes events related to the procedures involved.

Note 3: For users or other persons, this definition is restricted to events related to the use of investigational medical devices or comparators.

#### 7.1.2 Serious Adverse Event

Serious adverse event is an AE that led to any of the following:

- a) Death,
- b) Serious deterioration in the health of the subject, that resulted in any of the following:
  1. Life-threatening illness or injury,
  2. Permanent impairment of a body structure or a body function,
  3. Hospitalization or prolongation of patient hospitalization,
  4. Medical or surgical intervention to prevent life threatening illness or injury or permanent impairment to a body structure or a body function,
  5. Chronic disease

## Clinical Investigation Plan

- c) Fetal distress, fetal death or a congenital physical or mental impairment or birth defect.

Note: A planned hospitalization for pre-existing condition, or a procedure required by the CIP, without a serious deterioration in health, is not considered a SAE.

### 7.1.3 Device Deficiency

Device deficiency is defined as any inadequacy in the identity, quality, durability, reliability, usability, safety or performance of an investigational device, including malfunction, use errors or inadequacy in the information supplied by the manufacturer including labeling.

Note 1: The definition includes device deficiencies related to investigational medical device or the comparator.

Note 2: Cyber-security incidents related to the investigational product shall be reported as device deficiencies.

A device malfunction is the failure of an investigational medical device to perform in accordance with its intended purpose when used in accordance with the instructions for use or CIP, or IB.

## 7.2 Device Relationship

Determination of whether there is a reasonable possibility that an investigational product or device under investigation caused or contributed to an AE is to be determined by the Investigator and recorded on the appropriate CRF form. Determination should be based on assessment of temporal relationships, evidence of alternative etiology, medical/biologic plausibility, and patient condition (pre-existing condition).

### 7.2.1 Unanticipated Serious Adverse Device Effect

Unanticipated serious adverse device effect (USADE) refers to any serious adverse effect on health or safety or any life-threatening problem or death caused by, or associated with, a device, if that effect, problem, or death was not previously identified in nature, severity, or degree of incidence in the investigational plan or application (including a supplementary plan or application), or any other unanticipated serious problem associated with a device that relates to the rights, safety, or welfare of subjects.

### 7.2.2 Serious Health Threat

Serious Health Threat is a signal from any adverse event or device deficiency that indicates an imminent risk of death or a serious deterioration in the health in subjects, users or other persons, and that requires prompt remedial action for other subjects, users or other persons

Note: This would include events that are of significant and unexpected nature such that they become alarming as a potential serious health hazard or possibility of multiple deaths occurring at short intervals.

## 7.3 Adverse Event and Device Deficiency Reporting

### 7.3.1 Adverse Event Reporting

Safety surveillance and reporting starts as soon as the subject is enrolled in the clinical study. Safety surveillance and reporting will continue until the last follow-up visit has been performed, the subject is deceased, the subject concludes participation in the clinical study or the subject withdraws from the

## Clinical Investigation Plan

clinical study. Adverse event data, including deaths and device deficiency data, will be collected throughout the time period defined above and will be reported to the Sponsor on a CRF. Additional information with regard to an adverse event should be updated within the appropriate CRF.

Unchanged, chronic, non-worsening or pre-existing conditions are not AEs and should not be reported.

For the purposes of this study, the following event types will be reported:

1. All Adverse Events
2. All Adverse Device Effects
3. All Serious Adverse Events (whether or not the event is considered device or procedure related)
4. Unanticipated Serious Adverse Device Effects
5. All Device Deficiencies

Cardiac and non-cardiac related abnormal laboratory values will not be considered AEs unless:

1. the investigator determined that the value is clinically significant,
2. the abnormal lab value required intervention, or
3. the abnormal lab value required subject withdrawal from the clinical study.

An offline form will be made available to allow the investigator to report SAEs in the event the entry cannot be made in the Electronic Data Capture (EDC). This does not replace the EDC reporting system. All information must still be entered in the EDC system as soon as feasible.

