### 3.2.4 Adjudication of Adverse Events by an Independent Clinical Events Committee

An independent Clinical Events Committee (CEC), consisting of, at a minimum, an interventional cardiologist, cardiologist, cardiothoracic surgeon, and a neurologist will review and adjudicate pre-specified events reported by investigators in the clinical study as defined in the CEC Charter. Pre-specified clinical events defined in the primary and descriptive endpoints will be adjudicated according to the Valve Academic Research Consortium 2 (VARC-2) definitions. The CEC will have final adjudication responsibilities for subject outcomes related to primary and descriptive outcome measures.

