### 10.10.3 Clinical Events Committee (CEC)

The Clinical Events Committee (CEC) is an independent adjudication body comprised of qualified physicians (e.g., an interventional cardiologist, cardiothoracic surgeon, and a neurologist) who are not participants in the clinical study. The CEC will review and have final adjudication responsibilities for pre-specified adverse events reported by investigators or identified by Safety personnel for the clinical study as defined in the CEC Standards of Operation Charter and according to definitions provided in this CIP.

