**Stage 1**

Increase in serum creatinine to 150% to 199% (1.5 to 1.99 X increase compared with baseline) or increase of greater than or equal to ( $\geq$ ) 0.3 mg/dl ( $\geq$ 26.4 mmol/l) or Urine output <0.5 ml/kg per hour for > 6 but < 12 hours

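### Creatinine-defined acute kidney injury, chiefly stages 1–2, may be under-ascertained because the visible route to the CEC passes through an AE rule that filters laboratory values

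*Protocol*

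**What the plan says.** **Reporting rule.** Protocol 7.3.1 says that "Cardiac and non-cardiac related abnormal laboratory values will not be considered AEs unless" one of three conditions holds: "the investigator determined that the value is clinically significant"; "the abnormal lab value required intervention, or" "the abnormal lab value required subject withdrawal from the clinical study". The general definition in 7.1.1 is wider and counts "untoward clinical signs (including abnormal laboratory findings) in subjects, users or other persons" as adverse events.

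**CEC intake.** Protocol 3.2.4 says the CEC "will review and adjudicate pre-specified events reported by investigators in the clinical study as defined in the CEC Charter", and gives it the final word on primary and descriptive outcomes. Protocol 10.10.3 describes the intake more broadly, as "pre-specified adverse events reported by investigators or identified by Safety personnel for the clinical study".

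**AKI definition.** Appendix II grades AKI by change in creatinine from baseline up to 48 hours, with urine output as an alternative. Stage 1 opens with "Increase in serum creatinine to 150% to 199" per cent of baseline, or a rise of at least 0.3 mg/dl. Stage 2 is 200% to 299%. Renal replacement therapy counts as stage 3.

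**Use in the analysis.** AKI of any stage at 30 days is a descriptive endpoint (Protocol 4.3, SAP 1.4.4). Only stage 3 enters the secondary composite (Protocol 4.2, SAP 2.3.2). SAP 2.3.3 analyses descriptive endpoints on available data and gives no derivation of AKI.

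**Data collected.** Creatinine is drawn within 72 hours before the procedure (6.1.3), within 72 hours after it (6.3.1), and at discharge (6.4).

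**The concern.** AKI stages 1 and 2 can be reached by a laboratory value with no symptom and no treatment. That is the kind of finding that the 7.3.1 rule lets a site leave unreported. If the CEC sees only what sites report, whether such a case is counted depends on the investigator's view of its significance rather than on the Appendix II threshold. The study is single-arm, so the person forming that view knows which device was used.

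The plan describes its results beside published rates for approved devices. The composite is compared in this way explicitly, and the protocol's background section quotes stage 2/3 AKI rates for newer devices. Incomplete capture would make the observed AKI rate look better. The sensitivity analyses in SAP 2.13 would not show this, because they also start from CEC-adjudicated events.

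**Working it through.** The plan gives no figure to reproduce: neither AKI nor the composite carries a hypothesis test (Protocol 8.6), and no sample size rests on them. The check is a trace through the text, followed by a bounding calculation.

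**1. Can a qualifying case miss the CEC?** Take a subject whose creatinine rises by 0.3 mg/dl within 48 hours, who needs no treatment and stays in the study.
- Appendix II: stage 1 AKI is met.
- 7.3.1: not an AE, unless the investigator calls the value clinically significant.
- 3.2.4: if it is not reported, it is outside the stated intake.
- 10.10.3: Safety personnel may identify it, but no text requires creatinine values to be screened against Appendix II.
- SAP 2.3.2, 2.3.3 and 2.13: no step derives AKI from the laboratory data.

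So the visible rules permit the case to be lost.

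**2. Is this plausible in this population?** Exclusion criterion 18 admits creatinine up to 3.0 mg/dL. A rise of 0.3 is 0.3/3.0 = 10% of a baseline of 3.0, and 0.3/2.0 = 15% of a baseline of 2.0. A site could reasonably call a change of that size not significant, yet it meets stage 1.

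**3. Do the data for a check exist?** Mostly. Every subject should have a value before and a value after the procedure. However, 6.3.1 accepts a draw up to 72 hours while the AKI window closes at 48 hours. A subject whose only draw is at, say, 60 hours complies with the schedule but has no value in the window.

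**4. Size.** Expected cases = N × rate. Missed cases = N × rate × (1 − capture). N = 169 (Protocol 5.6). The stage 2/3 rate is 1.7%–2.8% (Protocol 1.1.1). Capture is not given in the documents; 50% to 90% is assumed.

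| Stage 2/3 rate | Expected of 169 | Missed at 90% | Missed at 75% | Missed at 50% |
|---|---|---|---|---|
| 1.7% | 2.87 | 0.29 | 0.72 | 1.44 |
| 2.8% | 4.73 | 0.47 | 1.18 | 2.37 |

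For scale, one case is 1/169 = 0.6 percentage points. The exact 95% interval is 0.37%–5.10% for 3/169 and 0.97%–6.77% for 5/169, so a loss of one or two cases is small beside the sampling error. In the Titan cohort (N = 60) the same rates give 1.02–1.68 expected cases, with 0.1–0.8 missed; one case there is 1/60 = 1.7 points.

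The documents give no stage 1 rate. At an assumed 5%–15%, 169 subjects give about 8.5–25 cases, and 50%–90% capture would miss about 0.8–12.7. Both inputs are assumptions, so this shows only where a sizeable loss could arise.

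**The case against.** The strongest reply is that the 7.3.1 filter concerns laboratory values, not diagnoses. AKI is a named endpoint with its own definition, and 15.2.1 lists it among anticipated adverse events. Section 3.2.4 says that events defined in the endpoints will be adjudicated, 7.3.1 itself requires all AEs to be reported, and 7.1.1 includes abnormal laboratory findings. On that reading a site should report any rise that meets Appendix II. There are also other safeguards: 10.10.3 gives Safety personnel a route of their own, section 11 provides for supplemental sponsor review, 11.3 has required laboratory reports annotated for clinical significance, and the CEC Charter, which is not among the documents, may contain laboratory triggers.

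Much of this stands, and it limits the point to a risk. A reader might infer that the CEC can see only investigator-reported events; 10.10.3 rules that out. It does not close the gap, however. The 7.3.1 wording has no exception for endpoint events, 7.1.1 and 7.3.1 pull in different directions, and annotation for significance under 11.3 is the same judgement over again. The Safety route is permitted, not required. A trigger in an unseen charter would help, but how an endpoint is ascertained should be readable from the protocol or SAP.

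A reader might also extend the point to bleeding or myocardial infarction. Appendix II does not support this: the hemoglobin criteria require overt bleeding, and peri-procedural infarction requires ischemic symptoms or signs as well as biomarkers.

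**Conclusion.** The stated rules allow creatinine-defined AKI, chiefly stages 1–2, to go unreported and unadjudicated. Under-ascertainment is possible; the documents do not show that it occurs, and its size cannot be determined from them. At the protocol's own stage 2/3 benchmark the loss would be about 0.3–2.4 of roughly 3–5 cases in 169, which rests entirely on an assumed capture of 50%–90%.

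A reader might reach a larger figure by taking the category of at least 10% for renal insufficiency or failure in Appendix XV and assuming that a share of it is lost. That is not supported. The category is not tied to the AKI stages or to the 48-hour window, it comes from literature and earlier studies whose capture methods are not described, and the share lost would be a guess.

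The effect on the secondary composite is probably small: it counts stage 3 only, and a subject who receives renal replacement therapy would plausibly meet the intervention condition. The primary endpoints, death and core-laboratory paravalvular leak, are unaffected. Bias against published rates is also unproven, because the documents do not show how AKI was ascertained in the comparator studies. The point is still worth correcting, because the remedy uses data that the protocol already requires.

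**What to change.** 1. In Protocol 3.2.4 and SAP 2.3.2/2.3.3, state that creatinine-based AKI stage is computed for every subject from the pre-procedure and post-procedure values that fall in the Appendix II window. Do not use every creatinine on file: the 30-day and 12-month values lie outside that window. Urine-output and renal-replacement criteria continue to come from site reports.
2. State that every qualifying rise goes to the CEC whether or not an AE was reported.
3. State in 7.3.1 that the laboratory-value filter does not apply to endpoint events.
4. Align the descriptions of CEC intake in 3.2.4 and 10.10.3.
5. Reconcile the 48-hour AKI window in Appendix II with the 72-hour post-procedure draw in 6.3.1, and report how many subjects have no value in the window so that they are not silently counted as free of AKI.

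The cost is one data listing and a few more CEC dossiers. The reported AKI rate may become less favourable.
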